3.3 Exposures

In CALGB/SWOG C80702, we will be collecting exposure data ranging from the primary intervention (celecoxib versus placebo) to tumor markers to blood markers to the diet and lifestyle questionnaire data. The questionnaire will be administered at 2 time points – within the first 6 weeks after randomization and within 14-16 months after randomization (~ 1.5 years after surgery). For these prevention substudies, exposures that are of particular interest include, but are not limited to:

1. Celecoxib versus placebo
2. Plasma vitamin D
3. Physical activity
4. Dietary pattern
5. Smoking history
6. Celecoxib or placebo (primary randomization in 80702)
7. Adiposity (body mass index and waist:hip ratio)
8. Vitamin intake (MVI as well as individual vitamins, including B6 & E)
9. Alcohol intake

4.0 DATA ANALYSIS

Data on the rates of adenomatous polyps, new primary colorectal cancer and new other primary cancers are drawn from older literature. Given the changes in incidences in certain cancers over the past several decades,³²² it will be important to define the rates of these events in current colorectal cancer survivors. We will collect data as described above. Alliance plans to incorporate similar data collection in other treatment trials. Exposure data will be stored in a central database that will allow for further studies of the influence of such host factors in cancer survivors.

Testing the exposures on the rates of polyps and new cancers will depend on the rates obtained in CALGB/SWOG C80702. For example, to estimate the incidence of second primaries, we expect to obtain follow-up colonoscopy data on 80% of patients without recurrence. Since 33% of patients are

expected to recur by year 4, 50% (n=1,250) is a conservative estimate. Two to 4% of these patients (25 to 50 patients) are expected to develop second primary cancers over the follow-up period. The incidence density rate will be estimated by the number of observed second primaries divided by the number of person years follow-up. Person-years follow-up is expected to be approximately 7,500 assuming 1,250 patients are followed for 6 years. The 95% confidence interval for the incidence density rate will be computed assuming a Poisson distribution for the number of observed secondary cancers and adjusting by the person-years follow-up.

The incidence of adenomatous polyps will be studied in the same patient population. Twenty to 30% of patients are expected to develop polyps within 3 years. If 80% of non-recurring patients have data on colonoscopy, we expect 250-375 pts with polyps. Approximately 50% of patients with colonoscopy data will receive treatment with celecoxib. Thus, the incidence density estimates by treatment with celecoxib will be based on approximately 625 patients per treatment group, with each patient (theoretically) followed for 6 years (3,750 person-years). The 95% confidence intervals for the incidence density estimates will be computed within each celecoxib treatment group as described above and compared.

In regard to neuropathy from oxaliplatin, an example of such an analysis is provided in [Appendix III](#) in which the AGXT 154 C->T polymorphism can be tested as impacting neuropathy after oxaliplatin.

In general, primary to any analyses, we will consider power for testing an exposure based on the number of events available (similar to methods utilized in prospective cohort studies). If power is inadequate for a specific comparison of interest, we will explore the inclusion of similar data from other trials for the analysis, if appropriate. Using logistic regression models, odds ratios and 95% CIs, we will measure associations with an exposure, adjusted for multiple potential confounders simultaneously.

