1.0 OBJECTIVES

- 1.1 Estimate the incidence density rate for each of second primary cancers and adenomatous polyps in colon cancer survivors.
- 1.2 Explore the impact of celecoxib, dietary factors, energy balance, physical activity, and vitamin D on second primary cancers and adenomatous polyps in colon cancer survivors.
- 1.3 Explore the role of celecoxib, physical activity, and vitamin supplementation on the incidence of peripheral neuropathy and time course of improvement/resolution.
- 1.4 Assess the influence of diet, body mass index, physical activity and other lifestyle habits on disease-free and overall survival among patients with stage III colon cancer (see [Appendix IV](#)).

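### Appendix V compares celecoxib with placebo on polyp incidence through two separate within-arm intervals, which gives no rate ratio, uses neither randomisation stratum, and is not linked to the general logistic model that follows

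*Combined protocol and SAP*

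**What the plan says.** Objective 1.2 of Appendix V is to "Explore the impact of celecoxib, dietary factors, energy balance, physical activity, and vitamin D on second primary cancers and adenomatous polyps" in colon cancer survivors. Section 4.0 (Data Analysis) first describes a one-sample method for second primary cancers: events divided by person-years, with a 95% interval "computed assuming a Poisson distribution for the number of observed secondary cancers and adjusting by the person-years follow-up".

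It then turns to polyps in the same patients. The number with colonoscopy data is set at half of the 2,500 enrolled: with 33% of patients "expected to recur by year 4, 50% (n=1,250) is a conservative estimate". On the polyp rate it says: "Twenty to 30% of patients are expected to develop polyps within 3 years", from which "we expect 250-375 pts with polyps". The estimates by celecoxib assignment rest on "approximately 625 patients per treatment group, with each patient (theoretically) followed for 6 years (3,750 person-years"). The celecoxib-specific method is one sentence: "The 95% confidence intervals for the incidence density estimates will be computed within each celecoxib treatment group as described above and compared". It names no rate ratio, rate difference, test or decision rule.

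The section closes with a general paragraph: "Using logistic regression models, odds ratios and 95% CIs, we will measure associations with an exposure, adjusted for multiple potential confounders simultaneously". Section 3.3 of the appendix lists celecoxib versus placebo first among the exposures of interest. The main protocol (5.6.2) stratifies the celecoxib randomisation by number of positive nodes and by current regular low-dose aspirin use.

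**The concern.** Two intervals, one per arm, describe each arm. They do not estimate the effect of celecoxib. A reader who wants the ratio of polyp rates and its precision would have to derive it.

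Comparing two intervals by eye is usually done by asking whether they overlap, and that is stricter than a 5% comparison. Non-overlap requires the estimates to differ by 1.96 × (SE₁ + SE₂), whereas a direct comparison requires 1.96 × √(SE₁² + SE₂²). A moderate true effect could be described as overlapping intervals, hence no difference.

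The crude intervals also leave out both stratification factors. Aspirin matters most here: sections 1.6 and 1.7 of the protocol report a 35% reduction in adenomatous polyps with aspirin in patients with previous colorectal cancer. That was at 325 mg daily, above the low dose that defines the stratum, so the relevance is plausible rather than shown.

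**Working it through.** **The plan's own figures.** All reproduce from Appendix V 4.0:
- Colonoscopy data: 2,500 × 0.67 × 0.80 = 1,340, taken down to 2,500 × 0.50 = 1,250.
- Patients with polyps, both arms together: 1,250 × 0.20 = 250 and 1,250 × 0.30 = 375.
- Per arm: 1,250 / 2 = 625 patients; 625 × 6 = 3,750 person-years.

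The appendix gives no significance level, effect size or power for this comparison.

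**Assumptions for the check.** 'Compared' is taken to mean non-overlap; the text does not say so. Rate ratios from 0.55 to 0.80 are assumed. Section 1.6 gives 0.55 to 0.76 for adenomas with COX-2 inhibitors, and its Table 1 gives 34% / 49% = 0.69 for celecoxib 400 mg daily. Person-years are equal in the two arms, and the total number of events is held at 250 or 375.

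**Level under a non-overlap rule.** With equal standard errors the critical value is z = 1.96 × 2 / √2 = 2.77, a two-sided level of 2 × (1 − Φ(2.77)) = 0.56%. Enumerating exact Poisson 95% intervals gives 0.46% at 250 events and 0.48% at 375.

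**Power, worked once by normal approximation (250 events, ratio 0.70).**
- Expected events: 250 / 1.70 = 147.1 on placebo and 102.9 on celecoxib.
- SE of the log rate ratio: √(1/147.1 + 1/102.9) = 0.1285. Effect: −ln 0.70 = 0.3567.
- Direct 5% comparison: Φ(0.3567/0.1285 − 1.96) = Φ(0.82) = 79%.
- Non-overlap threshold: 1.96 × (1/√147.1 + 1/√102.9) = 0.3548. Power: Φ((0.3567 − 0.3548)/0.1285) = Φ(0.015) = 51%.

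**Exact Poisson enumeration.** Non-overlap of exact intervals is set against a direct two-sided 5% test of the two counts, (x − y)/√(x + y).

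| Assumed ratio | 250 events: direct / non-overlap | Loss, points | 375 events: direct / non-overlap | Loss, points |
|---|---|---|---|---|
| 0.80 | 42.0% / 14.1% | 28 | 57.6% / 25.1% | 32 |
| 0.75 | 61.9% / 28.3% | 34 | 79.1% / 47.9% | 31 |
| 0.70 | 80.0% / 48.5% | 31 | 92.9% / 72.8% | 20 |
| 0.65 | 92.1% / 70.4% | 22 | 98.5% / 90.4% | 8 |
| 0.55 | 99.6% / 96.4% | 3 | about 100% / 99.8% | 0 |

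**Limit of the check.** The 250 to 375 count is for polyps within 3 years, while the person-years assume 6. Later polyps would add events and change the power figures, but would hardly move the 0.5% level.

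**Does the general logistic paragraph fill the gap?** It would give a direct effect with an interval, but on another scale. It takes no account of person-time, whereas the polyp paragraph and objective 1.1 work in incidence density. The scales also differ numerically: at an illustrative 25% versus 17.5%, the risk ratio is 0.70 and the odds ratio is (0.175/0.825) / (0.25/0.75) = 0.64.

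**The case against.** The strongest reply is that the section does plan a direct comparison. The closing paragraph of 4.0 promises adjusted odds ratios with 95% intervals for an exposure, and section 3.3 puts celecoxib versus placebo first in the list of exposures. This stands in part. A reader might infer from the polyp sentence that side-by-side intervals are the only between-arm method, or that no effect estimate for celecoxib would ever be reported. The documents do not support either inference. But the logistic paragraph is introduced as general, does not name polyps, and is not connected to the incidence-density comparison. Its adjustment is for unspecified confounders, not expressly for the randomisation strata.

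Second, the overlap rule is not in the text. A reader might conclude that the plan tests at the 0.5% level. It does not say that: it sets no rule and no level. The 0.5% figure describes one natural reading.

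Third, a flat loss of about 30 points might be inferred. The loss depends on an effect size the appendix does not state, and it nearly vanishes at the strong end of the background range. The 20 to 30% polyp rate also applies to both arms combined, so treating it as the placebo rate would understate the events.

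Fourth, the objective is exploratory, and the section says power will be considered from the events available. This stands, and it limits the consequence.

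**Conclusion.** The point holds in a limited form. The one method written specifically for celecoxib and polyps gives no effect estimate on the rate scale and uses neither stratification factor. The general logistic model does not resolve this, because it is on a different scale and is not linked to the comparison.

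The loss of power is conditional on reading the comparison as non-overlap and on the assumed rate ratio. With 250 to 375 events, it is 20 to 31 points at 0.70, 28 to 34 points at 0.75 to 0.80, and 0 to 3 points at 0.55. No confirmatory claim depends on this analysis, so the consequence is modest. A rate ratio with its own interval is nevertheless plainly better and can be had from the same data.

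**What to change.** In Appendix V 4.0, replace the polyp comparison sentence with wording such as: *Celecoxib and placebo will be compared by the incidence rate ratio with its 95% confidence interval, from a Poisson model with log person-years as offset and robust variance, including the celecoxib stratification factors (number of positive nodes, regular low-dose aspirin use). Arm-specific rates and intervals are descriptive. For celecoxib, this analysis replaces the general logistic regression described below.* If the sponsor prefers to keep the logistic model for celecoxib, the last sentence should call it supportive.

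Use the same approach for second primary cancers by celecoxib assignment.

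The cost is a few lines of text and slight extra analysis work. No new data are needed.

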Western-style diets have been hypothesized as contributing to the development of colon cancer.²⁷⁷ A factor analysis was conducted and two major dietary patterns: "prudent" and "Western" were identified. The prudent pattern was characterized by higher intakes of fruits, vegetables, legumes, fish, poultry, and whole grains, while the Western pattern, by higher intakes of red and processed meats, sweets and desserts, french fries, and refined grains. Increasing consumption of a Western diet was associated with an increased risk of colon cancer whereas increasing consumption of a prudent diet was associated with a reduced risk.^{83,278} In mouse models, a Western-style diet accelerates colon cancer progression and mortality.²⁷⁹⁻²⁸¹ Dietary factors have been associated with the risk of developing colon cancer but the influence of diet on patients with established disease is unknown. The association of dietary patterns with cancer recurrences and mortality was examined in 1009 patients with stage III colon cancer who were enrolled in a randomized adjuvant chemotherapy trial (CALGB 89803). A higher intake of a Western dietary pattern after cancer diagnosis was associated with a significantly worse disease-free survival (colon cancer recurrences or death). Compared with patients in the lowest quintile of Western dietary pattern, those in the highest quintile experienced an adjusted hazard ratio (AHR) for disease-free survival of 3.25 (95% confidence interval [CI], 2.04-5.19; P for trend <.001). The Western dietary pattern was associated with a similar detriment in recurrence-free survival (AHR, 2.85; 95% CI, 1.75-4.63) and overall survival (AHR, 2.32; 95% CI, 1.36-3.96], comparing highest to lowest quintiles (both with P for trend <.001). The reduction in disease-free survival with a Western dietary pattern was not significantly modified by sex, age, nodal stage, body mass index, physical activity level, baseline performance status, or treatment group.²⁸²

The influence of a Western pattern diet on the outcome of stage III colon cancer patients will be examined in the clinical trial. Moreover, the influence of pre- and post-diagnosis intakes of red meat, n-3 polyunsaturated fatty acids, and fruits and vegetables on survival will be examined.

- 3.4** In exploratory analyses, the effect of diet on chemotherapy-induced toxicity will be examined.

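### Appendix V names only logistic regression for exposure associations, with no time at risk or fixed horizon, although it defines second cancers and polyps as incidence densities

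*Combined protocol and SAP*

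**What the plan says.** One exploratory objective of Appendix V (section 1.0) is to "Explore the impact of celecoxib, dietary factors, energy balance, physical activity, and vitamin D on second primary cancers and adenomatous polyps in colon cancer survivors". Objective 1.1 in the same list asks for an incidence density rate for each of these outcomes.

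Section 4.0 then works in person-time. For second primaries, "The incidence density rate will be estimated by the number of observed second primaries divided by the number of person years follow-up", with a Poisson interval. For polyps by randomised arm, "The 95% confidence intervals for the incidence density estimates will be computed within each celecoxib treatment group as described above and compared".

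The closing paragraph of section 4.0, written as a general statement, turns to exposures: "Using logistic regression models, odds ratios and 95% CIs, we will measure associations with an exposure, adjusted for multiple potential confounders simultaneously". No other adjusted model is named in Appendix V. The sentence gives no offset, no fixed horizon and no rule for recurrence or death.

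The planning figures rest on patients who stay free of recurrence: "we expect to obtain follow-up colonoscopy data on 80% of patients without recurrence", and, with a third of patients "expected to recur by year 4, 50% (n=1,250) is a conservative estimate".

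**The concern.** A logistic model counts a patient observed for one year and one observed for six years alike: each either had the event or did not. That is harmless when the observation window is common to all, or unrelated to exposure. Here the window may be neither. The footnotes to section 6.0 end scheduled assessments at six years or at progression, whichever is first. The exposures listed in Appendix V section 3.3 include several that the trial and Appendix IV hypothesise will change DFS.

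If observation effectively stops at recurrence or death, an exposure that brings recurrence forward leaves less time in which a polyp or second cancer can be found. The odds ratio then moves below 1 with no biological effect, and the adverse exposure looks protective. An exposure that delays recurrence looks harmful.

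**Working it through.** **The plan's own figures.** All reproduce: 2,500 × 0.50 = 1,250 patients; 1,250 × 2–4% = 25–50 second primaries; 1,250 × 6 = 7,500 person-years; 1,250 × 20–30% = 250–375 patients with polyps; 625 × 6 = 3,750 person-years per arm. The strict product 0.80 × 0.67 × 2,500 = 1,340 confirms that 1,250 is conservative.

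**Inputs.**
- DFS: the yearly failure probabilities in section 13.1 (0.10, 0.12, 0.06, 0.05, 0.03, 0.02) give S = 1, 0.90, 0.78, 0.72, 0.67, 0.64, 0.62 at years 0 to 6. Failure by year 4 is 33%, as Appendix V states.
- DFS hazard ratios: 0.79 for celecoxib (section 13.1). For diet, Appendix IV section 3.3 reports that the highest Western-pattern quintile in an earlier trial "experienced an adjusted hazard ratio (AHR) for disease-free survival of 3.25" against the lowest. Values of 1.25 and 1.5 are assumed, to show a moderate range.
- Event rates λ, constant and the same in both exposure groups (no true effect). Second cancers at 2–4% over six years: −ln(0.98)/6 = 0.0034 to −ln(0.96)/6 = 0.0068 per year. Polyps at 20–30% within three years: −ln(0.80)/3 = 0.074 to −ln(0.70)/3 = 0.119 per year.

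**Assumptions.** Observation ends at recurrence, death or year 6. The exposure multiplies the DFS hazard by h. Polyps are dated continuously. For diet, hazard ratios rise geometrically across quintiles from 1 to 3.25 with average six-year DFS held at 0.62, which gives h = 0.531 in the lowest quintile and 0.531 × 3.25 = 1.725 in the highest.

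**Formulas.** With m_j = −ln(S_j/S_{j−1}):
- mean time at risk = Σ S_{j−1}^h (1 − e^{−h·m_j}) / (h·m_j)
- observed risk = Σ S_{j−1}^h e^{−λ(j−1)} · λ/(λ + h·m_j) · (1 − e^{−(λ + h·m_j)})
- odds ratio = odds of observed risk in the exposed ÷ odds in the reference.

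**Results with no true effect.**

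| Contrast | Mean years at risk (ratio) | Odds ratio, second cancers | Odds ratio, polyps |
|---|---|---|---|
| DFS HR 0.79 | 4.79 vs 4.52 (1.06) | 1.06 | 1.08–1.09 |
| DFS HR 1.25 | 4.22 vs 4.52 (0.93) | 0.93 | 0.92–0.91 |
| DFS HR 1.5 | 3.95 vs 4.52 (0.87) | 0.87 | 0.85–0.83 |
| Diet, top vs bottom quintile, HR 3.25 | 3.73 vs 5.15 (0.72) | 0.72 | 0.66–0.63 |

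Worked case, diet and second cancers at 4%: observed risks are 2.49% and 3.43%, so the odds ratio is (0.0249/0.9751) ÷ (0.0343/0.9657) = 0.72.

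**False-positive rate (nominal 5%, two-sided).** For the diet contrast with 250 per quintile (1,250/5) it is 7–9% for second cancers and 53–72% for polyps. With 500 per quintile (2,500/5) it is 9–14% and 82–95%.

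**After the change.** In 3,000 simulated data sets of the diet contrast (500 per quintile, 4% second cancers or 30% polyps), the person-time rate ratio was 0.98 for second cancers and 1.00 for polyps, with rejection of 5.2% and 5.0%.

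**The case against.** Several points on the other side are sound.

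- The sentence is general and follows the neuropathy paragraph. Near-identical wording in Appendix IV section 4.4 serves chemotherapy toxicity, where a binary model is ordinary. It may have been written mainly with such outcomes in mind. It is nevertheless the only adjusted model in Appendix V, and the paragraph is not limited to neuropathy.
- A reader might infer that the celecoxib comparison is biased. The documents do not support that: section 4.0 plans it on incidence density. Were logistic regression used at 625 per arm, rejection would be 5.2–5.4% for second cancers and 9–12% for polyps.
- A reader might also infer that time at risk is known to differ strongly by exposure. No passage says so. The strong difference comes from one extreme-quintile hazard ratio in an earlier trial.
- It is not settled that observation stops at recurrence. Section 5.9 asks for all colonoscopy reports in the first six years, Appendix V section 3.2 seeks other cancers throughout that period, section 14.2 requires all new malignancies to be reported, and section 6.0 keeps follow-up forms coming after progression for survival data. The distortion is therefore conditional.
- Among patients recurrence-free through six years, the simulated diet odds ratios were 0.97 and 1.00, with rejection of 4.7% and 4.3%. But the recurrence-free figure in section 4.0 is a planning estimate, not an analysis rule. Data are collected on all consenting patients, and selecting on later recurrence would condition on an outcome that the exposure may affect.
- Stakes are limited. With "Two to 4% of these patients (25 to 50 patients) are expected to develop second primary cancers over the follow-up period", false-positive inflation for second cancers is small.

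**Conclusion.** The point holds as a mismatch between model and outcome that can bias results, not as a demonstration that false associations will occur. Appendix V defines rates but names a model that ignores time. The size depends on two things the documents leave open: whether observation effectively ends at recurrence, and how strongly each exposure acts on DFS. With no true effect, spurious odds ratios run from 0.93–0.87 (second cancers) and 0.92–0.83 (polyps) at DFS hazard ratios of 1.25–1.5, to about 0.72 and 0.63–0.66 at the upper illustration of 3.25. Polyps carry the material risk because events are many. The analyses are exploratory, and neither the primary endpoint nor the planned celecoxib incidence-density comparison is affected.

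**What to change.** In Appendix V section 4.0:

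- For second cancers, replace logistic regression with Poisson regression with a log person-time offset, or Cox regression, censoring at death or last assessment. State whether follow-up after recurrence counts.
- For polyps, use an interval-based (complementary log-log) model by colonoscopy interval, because examination times vary between patients.
- State that the analysis population is all consenting substudy patients, each contributing their own time at risk.
- Keep logistic regression only for fixed-window outcomes such as neuropathy incidence.

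The colonoscopy and pathology reports and the follow-up forms needed are already required, so the cost is a wording change and slightly more analysis work.

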APPENDIX VI**IDEA PROSPECTIVE POOLED ANALYSIS****1.0 DESIGN**

IDEA is a prospective pooled analysis of individual patient data from multiple randomized trials conducted worldwide in the setting of stage III colon cancer. Each trial has randomized patients between 3 and 6 months of either FOLFOX or XELOX treatment. Specifically, for patients treated with FOLFOX, patients will be randomized to either 6 or 12 bi-weekly FOLFOX treatments. For patients treated with XELOX, patients will be randomized to either 4 or 8 three-weekly treatment cycles. Some trials have included a second randomization in a factorial design, others have included both stage II and III patients, and one trial (SCOT) has included rectal cancer patients. The primary IDEA analysis will include only stage III colon cancer patients, and in trials where a second randomization was present, the arms will be pooled over the second randomization. The primary endpoint is disease free survival, as defined below.

